## 1. VERSION HISTORY

This SAP for study C1071004 is based on the protocol amendment v1.0 (dated 14 February 2021).

**Table 1. Summary of Changes**

Version/ Date	Associated Protocol Amendment	Rationale	Specific Changes
1 18 Mar 2021	Amendment 1.0 14 Feb 2021	N/A	N/A

## 2. INTRODUCTION

This SAP provides the detailed methodology for summary and statistical analyses of the data collected in Study C1071004. This document may modify the plans outlined in the protocol; however, any major modifications of the primary endpoint definition or its analysis will also be reflected in a protocol amendment.

Any deviations from this analysis plan will be described in the Clinical Study Report (CSR).

C1071004 study protocol utilizes an umbrella study design. Combinations of PF-06863135, as a backbone therapy, with other anti-cancer therapies will be included in the protocol as sub-studies. Each sub-study is a stand-alone study including a Phase 1b and Phase 2 part. All the analyses will be performed independently for each sub-study.

The following sub-studies are included in this version of the SAP:

- Sub-study A (PF-06863135 + nirogacestat)

The planned interim analysis and the primary analysis for each sub-study will include all data up to a data cutoff date. For Part 2, the interim analysis for futility is planned after the first 25 participants are treated and followed for 2 post-baseline disease assessments in each sub-study. The primary analysis will be conducted once all participants have been followed for response for at least 6 months or have otherwise discontinued response assessments within the first 6 months of treatment in each sub-study. All summaries and analyses will include all data pertaining to visits/assessments performed up to and including the data cutoff date.

## 2.1. Study Objectives, Endpoints, and Estimands

## Phase 1b

Primary Objective	Primary Endpoints	Applicable Sub-study
To assess safety and tolerability of PF-06863135 in combination with other anti-cancer therapies in participants with RRMM in order to select a RP2D(s) for the combination	
 
DLTs during DLT observation period.
 
	
 
Sub-study A
 

Secondary Objectives	Secondary Endpoints	Applicable Sub-study
To evaluate the overall safety profile	
 
AEs as characterized by type, frequency, severity as graded by NCI CTCAE version 5.0, timing, seriousness, and relationship to PF-06863135 in combination with other anti-cancer therapies. The severity of CRS and ICANS will be assessed according to ASTCT criteria;
 
Laboratory abnormalities as characterized by type, frequency, severity (as graded by NCI CTCAE version 5.0), and timing.
 
	
 
Sub-study A
 

To evaluate anti-myeloma activity of PF-06863135 in combination with other anti-cancer therapies	
 
ORR and CCRR, per IMWG response criteria as determined by investigator;
 
Time to event endpoints: TTR, DOR, DOCCR and PFS per IMWG response criteria as determined by investigator, and OS;
 
MRD (assessed by central lab) negativity rate per IMWG sequencing criteria.
 
	
 
Sub-study A
 

To evaluate the PK of PF-06863135 given alone and in combination with other anti-cancer therapies. Additionally, PK of the combination partner will be	
 
PK parameters of PF-06863135: Cmax, Tmax, AUClast after PF-06863135 administration alone as a priming dose;
 
Pre- and post-dose concentrations of PF-06863135 in combination with other anti-cancer therapies;
 
	
 
Sub-study A
 

090177e196913362\Approved\Approved On: 19-Mar-2021 12:41 (GMT)

evaluated when administered with PF-06863135	
 
Trough serum concentrations of the combination partner at selected cycles.
 
	
To evaluate immunogenicity of PF-06863135 and combination partner(s) as applicable.	
 
Incidence and titers of ADA and NAb against PF-06863135 or combination partner(s) as applicable.
 
	
 
Sub-study A
 

Exploratory Objectives	Exploratory Endpoints	Applicable Sub-study
To explore the relationship between PF-06863135 and combination partners and the biology of the participant's MM.	
 
Measurements of biomarkers (DNA, RNA, protein or defined cell types) resulting from analyses of peripheral blood, saliva and/or BM biospecimens.
 
	
 
Sub-study A
 

To explore correlations between PF-06863135 exposure and efficacy, safety, and biomarker endpoints, if data allow.	
 
Selected PK, efficacy, safety, and biomarker endpoints.
 
	
 
Sub-study A
 

**Phase 2**

Primary Objectives	Primary Endpoints	Applicable Sub-study
To assess the clinical efficacy of PF-06863135 in combination with other anti-cancer therapies.	
 
ORR per IMWG response criteria as determined by investigator.
 
	
 
Sub-study A
 

Secondary Objectives	Secondary Endpoints	Applicable Sub-study
To determine additional efficacy outcomes of PF-06863135 in combination with other anti-cancer therapies.	
 
CCRR per IMWG criteria as determined by investigator;
 
Time to event endpoints: TTR, DOR, DOCCR and PFS per IMWG response criteria as determined by investigator, and OS;
 
MRD (assessed by central lab) negativity rate per IMWG sequencing criteria.
 
	
 
Sub-study A
 

090177e196913362\Approved\Approved On: 19-Mar-2021 12:41 (GMT)

To further characterize the overall safety profile and tolerability of PF-06863135 in combination with other anti-cancer therapies.
	
 
• AEs as characterized by type, frequency, severity as graded by NCI CTCAE, version 5.0, timing, seriousness, and relationship to PF-06863135 in combination with other anti-cancer therapies. The severity of CRS and ICANS will be assessed according to ASTCT criteria;
 
• Laboratory abnormalities as characterized by type, frequency, severity (as graded by NCI CTCAE version 5.0), and timing.
 
	
 
• Sub-study A
 

To evaluate PK of PF-06863135 at the RP2D in combination with other anti-cancer therapies. Additionally, to collect PK data of combination partner data when administered with PF-06863135.
	
 
• Trough concentrations of PF-06863135 and combination partners in selected cycles.
 
	
 
• Sub-study A
 

To evaluate immunogenicity of PF-06863135 and combination partner(s) as applicable.
	
 
• Incidence and titers of ADA and NAb against PF-06863135 or combination partner(s) as applicable.
 
	
 
• Sub-study A
 

Exploratory Objectives
	
Exploratory Endpoints
	
Applicable Sub-study


To assess the impact of PF-06863135 on patient-reported symptoms and health-related quality of life.
	
 
• EORTC QLQ-C30 and MY20.
 
	
 
• Sub-study A
 

To explore the relationship between PF-06863135 and combination partners and the biology of the participant's MM.
	
 
• Measurements of biomarkers (DNA, RNA, protein or defined cell types) resulting from analyses of peripheral blood, saliva and/or BM biospecimens.
 
	
 
• Sub-study A
 

To explore correlations between PF-06863135 exposure and efficacy, safety and biomarker endpoints, if data allow.
	
 
• Selected PK, efficacy, safety and biomarker endpoints.
 
	
 
• Sub-study A
 

090177e196913362\Approved\Approved On: 19-Mar-2021 12:41 (GMT)

### 2.1.1. Estimands (All Sub-studies)

#### Phase 1b

**Primary Estimand:** Dose-limiting toxicity (DLT) rate estimated based on data from DLT-evaluable participants during the DLT observation period (35 days from Cycle 0 Day 1 through Cycle 1 Day 28 ie, the 1-week period after the priming dose of PF-06863135 on Cycle 0 Day 1, plus 4 weeks of combination study intervention that begins on Cycle 1 Day 1). The estimand has the following attributes:

- Population: Relapsed/refractory multiple myeloma (RRMM) participants, as defined by the inclusion and exclusion criteria to reflect the targeted population of the treatment, who receive at least 1 dose of the study intervention in the Phase 1b part of the study and either experience DLT(s) during the DLT observation period or complete the DLT observation period without DLT. Participants without DLTs who receive less than the minimum requirement of the planned doses of each investigational product for reason other than treatment-related toxicity are not evaluable for DLTs. The minimum required exposure for DLT evaluability of PF-06863135 and the combination partner agent in the DLT observation period is specified in [Section 4](#).
- Variable: Occurrence of DLTs during the DLT observation period.
- Population-level summary measure: DLT rate defined as the number of DLT-evaluable participants with DLTs in the DLT observation period divided by the number of DLT-evaluable participants.

#### Phase 2

**Primary Estimand:** the treatment effect of PF-06863135 in combination with other partner agent on objective response rate (ORR) per the International Myeloma Working Group (IMWG) criteria as determined by investigator. The estimand has the following attributes:

- Population: RRMM participants, as defined by the inclusion and exclusion criteria to reflect the targeted population of the treatment, who received at least 1 dose of study intervention.
- Variable: Objective response defined as confirmed stringent complete response (sCR), complete response (CR), very good partial response (VGPR) and partial response (PR) per IMWG response criteria as determined by investigator, from the date of first dose until the first documentation of progressive disease (PD), death or start of new anti-cancer therapy.
- Intercurrent events: All data collected after an intercurrent event of subsequent anti-cancer therapy will be excluded. All response assessments regardless of gaps in disease assessments will be considered. Participants who do not have a post-baseline disease assessment due to early PD, who receive anticancer therapies other than the study intervention prior to achieving an objective response, or who die, experience

PD, or stop disease assessments for any reason prior to achieving an objective response will be counted as non-responders.

- Population-level summary measure: ORR defined as the proportion of participants in the analysis population with an objective response and 2-sided 90% confidence interval (CI) for ORR.

## 2.2. Study Design

This is a prospective, open-label, multi-center, parallel group, Phase 1b/2 umbrella study to evaluate safety, efficacy, PK, and pharmacodynamics of PF-06863135 in combination with other anti-cancer therapies in participants with RRMM. Each sub-study will be conducted independently, as new agents may be included in the future in additional sub-studies within the framework of this protocol.

Each combination will be assessed individually in 2 study parts:

- A Phase 1b part to evaluate the safety, tolerability, and select a recommended dose and regimen for the combination (combination RP2D).
- A Phase 2 part to further evaluate the efficacy and safety of the combination.

### Phase 1b Design:

The number of participants to be enrolled in each sub-study in Phase 1b will depend on the number of dose levels evaluated and the number of participants treated at each dose level. Phase 1b dosing (dose level to be evaluated in the next cohort) and enrollment (number of participants to be enrolled in the next cohort) decisions will be based on a Bayesian logistic regression model (BLRM) approach.

[figure not shown]
The Phase 1b part of the study will use an escalation approach to determine the RP2D of PF-06863135 when administered in combination with other anti-cancer therapies.

### Phase 2 Design:

Phase 2 will begin once the combination RP2D from the Phase 1b is selected. Approximately 50 participants will be enrolled in each sub-study in the Phase 2 part to assess anti-tumor activity and safety of PF-06863135 in combination with other anti-cancer therapies.

Each combination will proceed independently to Phase 2 to further evaluate the safety and anti-tumor activity.

**Figure 1. Study Design**

### 3. ENDPOINTS AND BASELINE VARIABLES: DEFINITIONS AND CONVENTIONS

#### 3.1. Primary Endpoints

##### 3.1.1. Phase 1b

The primary endpoint of the Phase 1b part of each sub-study is the DLTs during the DLT observation period, which is the first 35 days from Cycle 0 Day 1 through Cycle 1 Day 28 of study intervention.

##### 3.1.2. Phase 2

The primary endpoint in the Phase 2 part of each sub-study is ORR per IMWG response criteria, defined as the proportion of participants with an objective response per IMWG response criteria as determined by investigator.

Objective response is defined as having a best overall response (BOR) of confirmed sCR, CR, VGPR or PR.

For all efficacy endpoints per IMWG response criteria, BOR will be assessed based on reported overall responses recorded at evaluation time points from the date of first dose until the first documentation of PD, death or start of new anti-cancer therapy, whichever occurs first.

#### 3.2. Secondary Endpoints

##### 3.2.1. Efficacy Endpoints

##### 3.2.1.1. Cumulative Complete Response Rate

Cumulative complete response rate (CCRR) is defined as the proportion of participants with a cumulative complete response (CCR).

CCR is defined as having a BOR of confirmed sCR or CR per IMWG criteria as determined by investigator, from the date of first dose until the first documentation of PD, death or start of new anticancer therapy.

090177e196913362\Approved\Approved On: 19-Mar-2021 12:41 (GMT)

### **3.2.1.2. Duration of Response**

Duration of response (DOR) is defined, for participants with an OR per IMWG criteria as determined by investigator, as the time from the first documentation of OR that is subsequently confirmed, until PD per IMWG criteria, or death due to any cause, whichever occurs first.

### **3.2.1.3. Duration of Cumulative Complete Response**

Duration of cumulative complete response (DOCCR) is defined, for participants with a CCR per IMWG criteria as determined by investigator, as the time from the first documentation of CCR that is subsequently confirmed, until PD per IMWG criteria, or death due to any cause, whichever occurs first.

### **3.2.1.4. Progression-free Survival**

Progression-free survival (PFS) is defined as the time from the date of first dose until PD per IMWG criteria as determined by investigator, or death due to any cause, whichever occurs first.

### **3.2.1.5. Overall Survival**

Overall survival (OS) is defined as the time from the date of first dose until death due to any cause.

### **3.2.1.6. Time to Response**

Time to response (TTR) is defined, for participants with an OR per IMWG criteria as determined by investigator, as the time from the date of first dose to the first documentation of OR that is subsequently confirmed.

### **3.2.1.7. Minimal Residual Disease Negativity Rate**

Minimal Residual Disease (MRD) (assessed by central lab) negativity rate is the proportion of participants with negative MRD per IMWG sequencing criteria by bone marrow aspirate (BMA) at any time after first dose.

## **3.2.2. Safety Endpoints**

Adverse Events (AEs) will be characterized by type, severity, timing, seriousness, and relationship to study intervention.

AEs [except cytokine release syndrome (CRS) and immune cell-associated neurotoxicity syndrome (ICANS)] will be graded by the investigator according to the National Cancer Institute Common Terminology Criteria for Adverse Events (NCI CTCAE) version 5.0 and coded using the most current version of Medical Dictionary for Regulatory Activities (MedDRA).

Severity of CRS and ICANS will be assessed according to the American Society for Transplantation and Cellular Therapy (ASTCT) criteria and coded using the most current version of MedDRA.

Laboratory abnormalities will be characterized by type, severity (as graded by NCI CTCAE version 5.0) and timing. For laboratory tests without CTCAE grade definitions, results will be categorized as normal, abnormal, or not done.

### **3.2.3. Pharmacokinetic Endpoints**

#### **Phase 1b**

- PK parameters of PF-06863135:  $C_{max}$ ,  $T_{max}$ ,  $AUC_{last}$  after PF-06863135 administration alone as a priming dose;
- Pre- and post-dose concentrations of PF-06863135 in combination with other anti-cancer therapies;
- Trough serum concentrations of the combination partner at selected cycles.

#### **Phase 2**

- Trough concentrations of PF-06863135 and combination partners in selected cycles.

### **3.2.4. Immunogenicity Endpoints**

#### **Phase 1b**

- Incidence and titers of ADA and NAb against PF-06863135 or combination partner(s) as applicable.

### **3.3. Exploratory Endpoints**

#### **3.3.1. Translational Oncology Biomarkers**

- Measurements of biomarkers (DNA, RNA, protein, metabolites or defined cell types) resulting from analyses of peripheral blood, saliva and/or BM biospecimens.

#### **3.3.2. Patient-Reported Outcomes (Phase 2 Only)**

Patient-reported outcomes (PROs) are measured using the following instruments:

- European Organization for Research and Treatment of Cancer Quality of Life of Cancer Patients core module (EORTC QLQ-C30): EORTC QLQ-C30 is a well-known, reliable and valid self-administered questionnaire used in oncology trials. The QLQ-C30 contains 30 items and is grouped into five functional scales (physical, role, emotional, cognitive and social functioning), three symptom scales (fatigue, nausea/vomiting, and pain), six single items (dyspnea, insomnia, appetite loss, constipation, diarrhea and financial impact) and a global health status/quality of life (QoL) scale. The questionnaire uses 4-point Likert scales with responses from “not at all” to “very much” to assess all functioning and symptoms items and two 7-point Likert scales for overall health and overall QoL. Responses to all items are then converted to a 0 to 100 scale using a standard scoring algorithm. Higher scores on the functional scales represent higher levels of functioning. Higher scores on the

global health status/QoL scale represent higher health status/quality of life. Higher scores on symptom scales/items represent more extreme symptoms.

- European Organization for Research and Treatment of Cancer Multiple Myeloma module (EORTC QLQ-MY20): The QLQ-MY20 is a myeloma-specific module developed by the EORTC group specifically to assess quality of life in patients with multiple myeloma. It contains 20 items which use 4-point Likert scales, and are grouped into 2 functional scales (future perspective, body image) and 2 symptom scales (disease symptoms, side effects of treatment). Higher scores on the functional scales represent better functioning. Higher scores on the symptom scales/items represent more extreme symptoms.

### 3.4. Baseline Variables

#### **Start and end dates of study intervention:**

The date of first dose (start date) of study intervention in a combination therapy is the earliest date of the first nonzero dose date/time for each of the study drugs.

The date of last dose of study intervention in a combination therapy is the latest date of the last nonzero dose date for each of the study drugs.

#### **Definition of baseline:**

No windowing will be applied when defining baseline. For example, the protocol requires safety assessments to be performed within 28 days prior to first dose; however, values outside this window will not be excluded when determining baseline assessments. Any deviations from the protocol specified window will be documented as protocol deviations. A separate definition of adequate baseline will be provided for disease assessment related efficacy endpoints.

For all endpoints, the last assessment performed on or prior to the date of the first dose of study intervention will serve as the baseline assessment. If there are no observations meeting these criteria, then baseline is considered missing.

Participants who start treatment and discontinue from the study on the same day may have 2 different sets of data collected on Study Day 1 (one during study and one in the End of Treatment [EOT] visit). Data reported at the EOT visit are not eligible for baseline selection.

Triplicate ECGs are collected at all timepoints except screening (single ECG at screening); therefore, the baseline for ECG measurement is the pre-dose on Cycle 0 Day 1, or the most recent ECG assessment reported prior to the first administration of study drug. Unscheduled assessments will not be included in the calculation of the average. The average of the replicate measurements will be determined after the derivation of the individual parameters at each timepoint.

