### 3.5. Safety Endpoints

Safety endpoints will be summarized based on the on-treatment period unless otherwise specified.

On-treatment period is defined as the time from the first dose of study intervention through the minimum of [28 days after last dose, (start day of new anticancer therapy – 1 day)]. Anticancer therapy includes drug therapy and radiation with curative intent; the start of new anticancer therapy after the first dose of study intervention is derived as outlined in [Section 5.2.6](#). Adverse events occurring on the same day as the first dose of study intervention will be considered to have occurred during the on-treatment period. All other assessments which occur on the same day as the first dose of study intervention will be considered baseline assessments (see [Section 3.4](#) for the definition of baseline).

Safety data collected after the on-treatment period as described above will be listed but not summarized.

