### 5.2.11. Nominal and Unscheduled Visits

For all algorithms and analyses, visit labels as specified on the CRF will be used as the nominal timepoint (ie, assessment will not be slotted).

Unless otherwise specified, unscheduled assessments will not be displayed in summary tables by nominal visit/timepoint. Unscheduled assessments will be used when deriving baseline and worst case on-treatment for safety and PRO analyses (except where noted for baseline ECGs). Additionally, unscheduled assessments will be used for efficacy analyses (eg, defining date of progression/censoring, best overall response, date of last contact).

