### **6.7.3. Laboratory Data**

Laboratory results will be converted to International System of Units (Système International d'unités, SI) units which will be used for applying toxicity grades and for all summaries.

As described in [Section 3.4](#), baseline will be defined as the last assessment performed on or prior to date of the first dose of study intervention. If there are multiple assessments that meet the baseline definition on the same day without the ability to determine which was truly last, then the worst grade will be assigned as the baseline grade.

Results collected as strict inequalities (eg,  $>10$ ,  $<10$ ) will be converted to numeric values adding or subtracting a factor of  $<0.001>$ . Expressions of the form “ $\geq$ ” or “ $\leq$ ” will be converted to the end point. These numeric values will be evaluated for clinically significant abnormalities, but will not be included in calculations of summary statistics.

Additionally, laboratory results will be programmatically classified according to NCI-CTCAE version 5.0 grade. Non-numerical qualifiers will not be taken into consideration in the derivation of grade (eg, hypokalemia Grade 1 and Grade 2 are only distinguished by a non-numerical qualifier and therefore Grade 2 will not be derived). In summary statistics the number and percentage of participants corresponding to grades that only include non-quantitative criteria will be displayed as a blank or NA (not assessed) rather than 0. If there is any overlap between grade criteria (eg, CTCAE grading criteria for Creatinine

Increased – a value can fall into one range based on comparison to Upper Limit of Normal (ULN) and another range based on comparison to baseline), the highest (worst) grade would be assigned to that record. Grade 5 is defined in the CTCAE criteria guidance as an event with an outcome of death. Since laboratory data does not collect an outcome, Grade 5 is not used when programmatically grading laboratory data.

For laboratory tests without CTCAE grade definitions, results will be categorized as normal, abnormal, or not done.

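### Outside ECG and end-of-treatment data, baseline is set by calendar date, so an unscheduled post-dose laboratory result on the first-dose day can become baseline and drop out of the on-treatment laboratory summaries

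*SAP*

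**What the plan says.** Master SAP Section 3.4 sets one general rule that covers every endpoint. It reads: "the last assessment performed on or prior to the date of the first dose of study intervention will serve as the baseline assessment". Section 6.7.3 repeats it for laboratory data. Section 3.4 also says "No windowing will be applied when defining baseline", so how old a value is does not disqualify it.

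Section 3.5 opens the safety window at dosing, in the words "On-treatment period is defined as the time from the first dose of study intervention through the minimum of". The two limits then compared are the 28-day point following the last dose and the day before any new anticancer therapy. It then splits the first-dose day by type of data. For events, "Adverse events occurring on the same day as the first dose of study intervention will be considered to have occurred during the on-treatment period". For the rest, "All other assessments which occur on the same day as the first dose of study intervention will be considered baseline assessments".

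Two further rules matter. Section 5.2.11 says "Unscheduled assessments will be used when deriving baseline and worst case on-treatment for safety and PRO analyses", with an exception for baseline ECGs. Section 6.7.3 covers same-day laboratory results whose order cannot be established: "then the worst grade will be assigned as the baseline grade".

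Section 3.4 makes two exceptions of its own. ECG baseline must come before the first administration, and results from an end-of-treatment visit on Day 1 cannot be baseline. No such protection is given to laboratory results. The Sub-study A and Sub-study B SAPs both refer to master Sections 3.4 and 3.5 for these definitions.

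**The concern.** A baseline value should describe the participant before treatment. Under a date-only rule, a sample taken hours after the first injection qualifies as baseline, and because the last qualifying value is used, it displaces the pre-dose one. Section 3.5 also takes it out of the on-treatment period, although that period starts at the first dose.

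The laboratory outputs in Section 6.7.3 are at stake: the shift tables by maximum on-treatment grade, the table of moves from Grade 2 or lower to Grade 3 or higher, the on-treatment liver-test counts, and the liver listings triggered by post-baseline values. A change caused by treatment could appear there as a condition the participant already had.

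The situation can arise. Protocol Section 8.2.5 allows unscheduled laboratory tests at any time for a perceived safety issue.

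**Working it through.** The plan gives no figure for this point, so there is none to reproduce. The check applies the rules to a result obtained after dosing on the first-dose day.

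**By type of data**

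- *Laboratory, sample order known.* The later sample is the last on that date, so it becomes baseline (3.4, 6.7.3). Section 3.5 classes it as a baseline assessment, so it does not enter the on-treatment maximum.
- *Laboratory, sample order unknown.* The worst grade of the day becomes baseline (6.7.3). If the post-dose value is the worse one, the result is the same as above.
- *ECG.* The pre-dose baseline stands (3.4). Section 3.5 still calls a same-day post-dose ECG a baseline assessment, so it is unclear whether it enters the on-treatment QTcF maximum in Section 6.7.5.
- *End-of-treatment visit on Day 1.* Barred from baseline by Section 3.4, yet called baseline by Section 3.5.
- *Adverse events.* On-treatment, so not lost.
- *Vital signs.* Listed only (6.7.4), so there is no summary to drop out of.

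Scheduled assessments are largely protected. Protocol Sections 8.2.1 to 8.2.3 place physical examinations, vital signs and ECGs before dosing, and Section 8.2.5 has laboratory reports reviewed before dosing. The exposure is therefore to unscheduled laboratory results.

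**Effect on the shift from Grade 2 or lower to Grade 3 or higher (assumed grades, sample order known)**

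| Pre-dose | Post-dose, same day | Later maximum | SAP rule | Date/time rule |
|---|---|---|---|---|
| 1 | 3 | 3 | 3 to 3, not counted | 1 to 3, counted |
| 1 | 3 | 2 | 3 to 2, not counted | 1 to 3, counted |
| 3 | 2 | 3 | 2 to 3, counted | 3 to 3, not counted |

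In row 1 the on-treatment maximum is still Grade 3, and only the shift is lost. In row 2 the Grade 3 value survives in the summaries only as a baseline grade. Row 3 shows the error running the other way. If order were unknown, rows 1 and 2 would come out as shown. Row 3 would give baseline Grade 3, in agreement with the date/time rule.

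**Scale per participant.** Sub-study A Phase 2 plans about 50 participants, so one misclassified participant moves a percentage by 1/50 = 2 points. The Sub-study B expansion has at most 20, so one participant is at least 1/20 = 5 points. These are sizes per case. The documents do not give the number of cases.

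**The case against.** The strongest reply is that the gap is narrow and the safety signal is captured elsewhere. Most of this stands. Protocol Section 8.2.5 requires clinically relevant laboratory changes to be recorded as adverse events, and adverse events on the first-dose day count as treatment-emergent. Potential Hy's Law cases are reported as serious adverse events (Protocol Appendix 6). Every laboratory value is listed with its grade. An abnormality that persists to a later sample still reaches the on-treatment maximum. The additional samples the protocol specifies for suspected CRS are for PK, circulating proteins and cytokines, which are not CTCAE-graded safety tests. None of this corrects the shift tables or liver-test counts, which are derived from the laboratory data.

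Three stronger readings are tempting, and the documents do not support them.

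- A reader might infer that any post-dose result that day is lost. The ECG and end-of-treatment exceptions, the adverse-event rule and the listing-only treatment of vital signs rule that out.
- A reader might infer that the error always hides toxicity. The general rule takes the last value, not the worst, so an improved post-dose value would lower the baseline and inflate later shifts.
- A reader might take the transient lymphocyte decreases in Protocol Section 2.2.3.1 as evidence that this will happen often. Those findings come from cynomolgus monkey studies and say nothing about human values within hours of a dose.

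The reach into Sub-study B also needs care. Laboratory abnormalities are a primary endpoint of its expansion part, and its SAP cites master Sections 3.4 and 3.5. It also cites master Section 6.5.1 for baseline summaries and 6.6 for safety, which are 6.6.1 and 6.7 in the master SAP supplied, a document that covers only Sub-study A. A different master SAP may govern it.

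**Conclusion.** The point holds for laboratory data. As written, a worsened unscheduled result obtained after dosing on the first-dose day becomes the baseline grade whether or not the sample order is known. It then leaves the on-treatment shift and liver-test summaries. This is a stated rule that gives a wrong answer, not a missing detail.

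It is a minor point. The frequency cannot be computed from the documents and is probably low, because it requires an unscheduled safety laboratory test after dosing on that one calendar day. The distortion can run either way. It runs toward masking when the value has worsened, and where order is unknown the tie rule can only keep or raise the baseline grade. The conclusion assumes that the program follows the SAP wording literally and, for Sub-study B, that the governing master SAP contains the same wording.

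**What to change.** In master SAP Sections 3.4, 3.5 and 6.7.3:

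- Define baseline as the last non-missing assessment before the date and time of first dose. The SAP already refers to both times needed: Section 3.4 derives the first dose from "the first nonzero dose date/time for each of the study drugs", and the Section 6.7.3 laboratory listing is sorted by collection date and time.
- Count same-day results timed after first dose as on-treatment.
- Treat untimed same-day records as pre-dose when they belong to a visit the protocol schedules before dosing. Flag untimed unscheduled same-day records for review. Automatic assignment either way would be wrong for some of them: calling them all on-treatment would turn a pre-dose repeat test into apparent toxicity.
- Limit the worst-grade tie rule to samples known or scheduled to be pre-dose.
- Reconcile the same-day sentence in Section 3.5 with the ECG and end-of-treatment rules in Section 3.4, and say where a post-dose ECG on the first-dose day belongs.
- Use the same wording in whichever master SAP governs Sub-studies A and B.

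The cost is a few sentences, one date/time comparison in the program and manual time review of a small number of records.
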